Group 2: Participants with *M. tuberculosis* harboring neither *inhA* nor *katG* resistance mutations. During Stage 1, eligible participants will be enrolled in Step 1 only. During Stage 2, participants who meet Step 1 and Step 2 entry criteria will be enrolled as positive controls. Also during Stage 2, participants not eligible to enter Step 2 and participants recruited after Step 2 accrual targets have been met may be enrolled in Step 1.

Group 3: Participants with an *M. tuberculosis* isolate with a *katG* mutation (with or without an *inhA* mutation), associated with high-level resistance. **During Stage 2, participants who meet Step 1 and Step 2 entry criteria will be randomized 1:1 to receive either INH 15 mg/kg or 20 mg/kg daily for 7 days. Participants who do not meet Step 2 criteria will be enrolled in Step 1 only.**

Participants who are screened for the study, but are not eligible to receive study treatment will be referred without delay for appropriate treatment. Those who are registered or randomized to receive treatment will be referred without delay to appropriate treatment after completing study treatment (no later than Day 10).

DURATION Approximately 23 days

SAMPLE SIZE Among participants eligible to participate in Step 1 only, accrual targets are as follows:

Group 1: Minimum of 16 to a maximum of 70
Group 2: Minimum of 48 to a maximum of 64
Group 3: Minimum of 64 to a maximum of 84

These participants may be enrolled during Stages 1 or 2.

Among participants eligible to enroll in Step 1 and Step 2, accrual targets are as follows:

Group 1: 48 evaluable participants (16 completing treatment in each dosing cohort). During Stage 1, 15 Group 1 participants will be enrolled (5 per dosing cohort). Once it is determined that the study is feasible, Stage 2 will begin and an additional 33 Group 1 participants will be randomized (11 participants added to each cohort, for a total of 16 participants per cohort).

Group 2: 16 evaluable participants will be followed as a fourth Step 2 cohort, enrolled during Stage 2.

Group 3: 20 evaluable participants (10 completing treatment in each dosing cohort) will be randomized.

At the end of Stage 1, the sample size for enrollment in the treatment cohorts may be increased up to 88 evaluable participants (22 in each treatment cohort) if the standard deviations of the primary endpoint from Group 1 are larger than expected.

Schema Table 1: A5312 Accrual Targets					

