3.0 STUDY DESIGN

This is a two-stage, two-step, phase IIa, open-label, randomized clinical trial among adult participants with sputum smear positive pulmonary TB evaluating the EBA of three different doses of INH among participants infected with *M. tuberculosis* with *inhA* mutations (Group 1). In addition, the EBA of INH among participants with *M. tuberculosis* with no genotypic evidence of INH resistance (Group 2) will be determined. Among participants infected with an *M. tuberculosis* strain with *katG* mutations (Group 3), **the EBA of INH at a dose of 15 or 20 mg/kg will be determined. These doses are selected because doses of up to 15-20 mg/kg appear to be safe (in other studies, as well as in the 15 mg/kg dosing cohort in Group 1 in the current trial) and the safety of doses higher than 20 mg/kg has not been established. In addition, upon preliminary assessment of the EBA data in the *inhA* arms, INH demonstrated activity, and this activity appeared to be dose-related.**

No study drug is administered under Step 1. Data collected in Step 1: (a) determine eligibility to Step 2, and (b) allow characterization of INH MICs in three groups (secondary objective). Groups 1, 2, and 3 consist of participants infected with TB with *inhA* mutations, with DS-TB and with TB with *katG* resistance-conferring mutations, respectively.

The study's primary objectives are addressed via Step 2 evaluations. Participants enrolling to Step 2 receive the study drug, INH, which will be given with vitamin B6 ≥ 25 mg daily, by mouth. During both stages, participants in Group 1 who meet Step 2 entry criteria will be randomized to receive 5, 10, or 15 mg/kg of INH daily for 7 days. During Stage 2, participants in Group 2 who meet Step 2 entry criteria will receive 5 mg/kg of INH daily for 7 days. **During Stage 2, participants in Group 3 who meet Step 2 entry criteria will be randomized 1:1 to receive 15 or 20 mg/kg of INH daily for 7 days.** After completion of 7 days of INH alone, participants will be referred to begin standard anti-TB chemotherapy according to South African TB Control Programme Guidelines.

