4.5.2 Registration/Randomization

For participants from whom informed consent has been obtained, but who are deemed ineligible or who do not enroll into the initial protocol step, an ACTG Screening Failure Results form must be completed and keyed into the database.

Patients who are eligible for participation in the study based on screening results will be registered to the protocol at the time of enrollment.

During Stage 1, Group 1 participants who meet Step 2 entry criteria will be randomized 1:1:1 to one of three doses of INH (5, 10, or 15 mg/kg). Group 1 participants who do not meet Step 2 entry criteria, as well as Group 2 and 3 participants will be enrolled in Step 1, but will not receive study drug. They will be discontinued from the study after their Step 1, Day 0 visit and referred for standard local TB treatment.

During Stage 2, Group 1 participants who meet Step 2 entry criteria will be randomized as during Stage 1. Group 2 participants who meet Step 2 entry criteria will be registered and assigned to receive 5 mg/kg study drug daily.

Group 3 participants who meet Step 2 entry criteria will be randomized 1:1 to receive 15 mg/kg or 20 mg/kg study drug daily. Group 1, 2, or 3 participants who do not meet Step 2 entry criteria will be enrolled in Step 1, but will not receive study drug. They will be discontinued from the study after their Step 1 Day 0 visit and referred for standard local TB treatment.

During Stage 2, enrollment of Group 2 participants will proceed so that, on average, for every two Group 1 participants enrolled in Step 2 per month, one Group 2 participant will be enrolled. The enrollment for Group 2 will be controlled by setting a recruitment limit, and it will be manually adjusted by the data manager and statisticians routinely (e.g., every month or twice per month).

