For Group 1 cohorts, the sample size of 16 is required for a two-sided 95% CI with a precision (half-width) of less than or equal to 0.064 with SDs between 0.060 and 0.120. This means that, for example, if the mean of EBA₀₋₇ (CFU) from the 15 mg/kg of INH for participants with an *inhA* mutation is 0.1 and the SD is 0.12, there is 95% probability that the CI of 0.04 and 0.17 covers the true mean.

Similarly, if the mean of EBA₀₋₇ (CFU) from Group 2 is 0.2 and the SD is 0.12, there is 95% probability that the CI of 0.14 and 0.26 covers the true mean.

This sample size should allow for evaluation of the association between AUC/MIC and EBA₀₋₇, one of the other primary analyses, with high precision, as the data from all experimental dosing cohorts will be pooled for this PK/PD analysis [9, 13, 15, 42].

For Group 3, the sample size of 10 per dosing cohort was selected since the analysis of EBA₀₋₇ (TTP) per dosing cohort will be exploratory. Assuming the SD for Group 3 cohorts will be 6, which is the overall SD of EBA₀₋₁₄ (TTP) from the previous ACTG EBA study (A5307, unpublished), a half-width of a 95% CI is 0.086 with the sample size of 10. This means, for example, if the mean of EBA₀₋₇ (TTP) from a dosing cohort in Group 3 is 13, there is 95% probability that the CI of 9.28 and 16.7 covers the true mean. A possible dosing effect for this group will be examined through visual displays.

Accrual:

During Stage 1, five participants were recruited to each cohort in Group 1. During Stage 2, 11 additional participants will be recruited to each cohort in Group 1, **20 participants in Group 3**, and 16 participants in Group 2 will be recruited. In the final analyses, the data from both stages will be combined. The time to accrual for this study (Stage 1 and 2 combined) is approximately **4 years**.

To maintain desired precision of estimation (primary analyses), participants who discontinue the study prior to the Day 7 evaluations will be replaced. All data from every randomized participant will be stored in the study database, and will be examined for the final analyses.

Participants enrolling to Step 1 only will be considered evaluable if all data that are required are available at screening and/or entry regardless of subsequent known or unknown loss to follow up.

Table 9.4-2: A5312 Accrual Targets

	Resistance Mutation	Participants Completing Step 1 Only ¹	Participants Completing Step 1 and Step 2 ²		Total Participants

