## 2.2 Major Protocol Revisions

Version 2.0 of the study protocol had two Letters of Amendments (LOA). One additional LOA was approved by the TB TSG Steering Committee in September 2016 to improve accrual. Version 3.0 of the protocol was finalized on March 15, 2018. The list below summarizes the main purposes of the LOAs and the changes in Version 2.0 from Version 1.0 and in Version 3.0 from Version 2.0.

- LOA#1 (dated May 4, 2013) – approved on September 17, 2015

The main purpose was to modify the protocol to reflect the decision to conduct A5312 as a non-IND study.

- LOA #2 (dated January 16, 2015) – approved on September 17, 2015

The main purpose was to relax the Step 2 entry criteria to improve recruitment. The changes included, 1) HIV-positive candidates with CD4+ cell count of  $\geq$ 50 cells/mm^3 (instead the original cut off of 200 cells/mm^3) are eligible for the study, and 2) The exclusion of current treatment, or treatment within 30 days prior to entry, with antiretroviral therapy (ART) or expected to initiate ART within 8 days after Step 2 entry has been removed.

- Protocol Version 2.0 (dated August 18, 2015)

The main changes were to increase the target accrual for Groups 1 and 2 during Step 1 (the target accrual for Groups 1 and 2 during Step 2 remains the same), to change the consent forms, to change the inclusion criteria for Group 3 to allow participants who have a katG mutation with or without an inhA mutation to enter study, and update protocol for the completion of Stage 1.

- LOA #1 after Protocol Version 2.0 (dated October 2016) – approved by the TB TSG Steering on September 28, 2016

The main changes were to relax the exclusion criteria on usage of second-line anti-TB drugs and/or antibiotics intended for bacterial treatment prior to Step 1 screening (relaxed Section 4.4.2 and removed Section 4.4.3 of the protocol).

- Protocol Version 3.0 (dated August 21, 2018)

The main purpose of this amendment was to add a treatment cohort for participants with *katG* mutation (Group 3) randomizing them 1:1 to receive either INH 15 mg/kg (n=10) or INH 20 mg/kg (n=10) daily, plus vitamin B6  $\geq$ 25 mg daily for 7 days. Accrual targets were increased for Group 3 to recruit eligible participants.

- LOA #1 for Protocol Version 3.0 (dated August 3, 2020)

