## 4.3 Analyses of Outcomes Measures

### 4.3.1 Primary outcomes

This is a per-protocol analysis in the efficacy population defined in Section 3.1. The primary endpoint is EBA0-7(CFU), which is defined in Section 3.2. Descriptive statistics of EBA0-7(CFU) with N, mean (s.d.), median (IQR), min, and max for each of the cohorts will be reported. Box plot of EBA0-7(CFU) with Q1, median, mean, and Q3 and plot with 95% confidence intervals for the mean EBA0-7(CFU) will be created for each cohort. Note: The analysis for this outcome will be performed for Group 1 and Group 2.

Another primary endpoint is EBA0-7(TTD), which is defined in Section 3.2. Descriptive statistics of EBA0-7(TTD) with N, mean (s.d.), median (IQR), min, and max will be reported by each cohort. Box plot of EBA0-7(TTD) with Q1, median, mean, and Q3 and plot of 95% confidence interval for the mean EBA0-7(TTD) will be created for each cohort.

New grade 2 or higher signs and symptoms, as well as laboratory events will be summarized in a table using SMR. In addition, all new grade 2 or higher signs/ symptoms and laboratory events with relatedness of treatment and most related drugs.

The PK analysis to examine the relationship between the AUC/MIC and the EBA as described in the protocol Section 9.2.1.2 will be provided in a separate PK analysis plan.

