### 4.3.2 Secondary outcomes

Descriptive statistics of MICs with N, mean (s.d.), median (IQR), min, and max will be summarized by mutation Group (inhA mutation, katG mutation, or neither of these mutations). Box plot of MICs by mutation Group with Q1, median, mean, and Q3, histogram to examine possible bimodal distributions, and plot of 95% confidence interval for the mean MICs by mutation Group will be created.

Nonlinear mixed model using SAS procedure NLMIXED will be fit to estimate the decrease of log10 CFU counts per day for the 'early' and 'terminal' phase. If there is no clear bi-phase pattern, linear mixed model using SAS procedure MIXED will be used. All available log10 transformed CFU counts at all time points will be included as a dependent variable, and day of the samples will be included as the primary exploratory variable in the model for each cohort. Note: The analysis for this outcome will be performed for Group 1 and Group 2.

Nonlinear mixed model using SAS procedure NLMIXED will be used to estimate the increase of TTD per day for the 'early' and 'terminal' phase. If there is no clear bi-phase pattern, linear mixed model using SAS procedure MIXED will be used. Log10 transformation may be applied if appropriate. TTD from all time points (excluding results from contaminated samples or re-culture of contaminated samples after addition decontamination) will be included as a dependent variable, and day of the sample will be included as exploratory variable in the model for each cohort.

Additional analyses will be conducted:

- Descriptive statistics of EBA0-2(CFU) with N, mean (s.d.), median (IQR), min, and max for each of the cohorts will be reported. Box plot of EBA0-2(CFU) with Q1, median, mean, and Q3 and plot

with 95% confidence intervals for the mean EBA0-2(CFU) will be created for each cohort. Note: Note: The analysis for this outcome will be performed for Group 1 and Group 2.

- Descriptive statistics of EBA2-7(CFU) with N, mean (s.d.), median (IQR), min, and max for each of the cohorts will be reported. Box plot of EBA2-7(CFU) with Q1, median, mean, and Q3 and plot with 95% confidence intervals for the mean EBA2-7(CFU) will be created for each cohort. Note: The analysis for this outcome will be performed for Group 1 and Group 2.

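### Group 3 is randomized between 15 and 20 mg/kg, but no planned analysis estimates the between-dose difference in EBA0-7(TTD) with its uncertainty

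*Protocol*

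**What the plan says.** SAP 2.2 describes Version 3.0 this way: "The main purpose of this amendment was to add a treatment cohort for participants with" a katG mutation. Protocol 4.5.2 sets the allocation: "Group 3 participants who meet Step 2 entry criteria will be randomized 1:1 to receive 15 mg/kg or 20 mg/kg study drug daily." The protocol schema gives the size: "Group 3: 20 evaluable participants (10 completing treatment in each dosing cohort) will be randomized."

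Protocol 9.4 explains the choice of 10 per dose by saying that the EBA0-7 (TTP) analysis "per dosing cohort will be exploratory", and then gives the one stated method for the dose effect: "A possible dosing effect for this group will be examined through visual displays." I read TTP and TTD as the same measure.

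The rest of the Group 3 efficacy output is by cohort:

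- Protocol 9.6.1.2 plans descriptive statistics, box plots and six cohort CIs.
- SAP 4.3.1 plans N, mean, SD, median, IQR and range, plus a "plot of 95% confidence interval for the mean EBA0-7(TTD) will be created for each cohort".
- SAP 4.3.2 plans mixed models of TTD in which "day of the sample will be included as exploratory variable in the model for each cohort".

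Exposure is handled separately. Protocol 9.2.1.3 and 9.6.1.3 relate AUC/MIC to EBA and include Group 3 TTD. Protocol 9.6.2.3 adds an exploratory simulation of target attainment at 15 or 20 mg/kg. SAP 4.3 defers the PK analyses to a separate plan.

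**The concern.** Randomization makes the 20-versus-15 contrast the one unconfounded dose comparison in Group 3, and the protocol names a dosing effect as something to look at. Protocol 2.2 also asks at what dosage isoniazid might overcome inhA or katG resistance. Protocol 3.0, after its safety reasons, cites preliminary Group 1 data in which "INH demonstrated activity, and this activity appeared to be dose-related". Readers of the Group 3 report will therefore look for a dose pattern.

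The plan gives them two cohort means, each with its own interval, and no difference with an interval. With 10 per dose, a chance gap may be described as a trend, or a real gap may be dismissed because the cohort intervals overlap. Neither reading tells anyone how large a dose effect the data still allow. A contrast computed after the plots have been seen carries less weight than one named beforehand.

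**Working it through.** **Inputs.** n = 10 evaluable per dose (protocol schema and 9.4). SD = 6 (protocol 9.4, taken from EBA0-14 in an earlier study). Example mean = 13 with CI 9.28 to 16.7 and stated half-width 0.086 (protocol 9.4). The documents give no effect size, power or error rate for 15 versus 20 mg/kg.

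**The plan's own figure, one cohort.**

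- With z: 1.960 × 6/√10 = 3.72, so 13 ± 3.72 = 9.28 to 16.72. This reproduces the example CI.
- With t on 9 df: 2.262 × 6/√10 = 4.29, so 8.71 to 17.29.
- The stated half-width of 0.086 is not reproduced from SD 6. It equals the Table 9.4-1 entry for SD 0.12 and n = 10: 2.262 × 0.12/√10 = 0.0858. This is a separate error, and the present point does not depend on it.

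**The figure the plan does not give, the difference between doses.**

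- SE = SD × √(2/n) = 6 × √0.2 = 2.68.
- 95% half-width with t on 18 df: 2.101 × 2.68 = 5.64 (with z, 5.26).
- Relative to the example mean: 5.64/13 = 43%.

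| Assumed SD | SE of difference | 95% half-width (t, 18 df) |
|---|---|---|
| 3 | 1.34 | 2.82 |
| 6 (protocol) | 2.68 | 5.64 |
| 9 | 4.02 | 8.46 |

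**What this means for reading the plots.** At SD 6, an observed gap of 3 units has the interval 3 ± 5.64 = -2.6 to 8.6. A gap of one third of the example mean, 4.33, has the interval -1.3 to 10.0. Both are compatible with no effect and with a large one.

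**Why the cohort intervals do not substitute.** If both sample SDs are 6, the two plotted t intervals separate only when the means differ by more than 2 × 4.29 = 8.58. The interval for the difference already excludes zero beyond 5.64. Judging by eye whether the intervals overlap therefore answers a different question.

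**Direction.** Protocol 9.2.1.2 and SAP 3.2 define EBA0-7(TTD) as (baseline − Day 7)/7. A drug that lengthens TTD gives a negative value. The worked example uses +13, and SAP 4.1 and 4.3.2 describe the model slope as an increase in TTD. The sign does not change any half-width, but it decides which cohort looks more active.

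**The case against.** The strongest case for the plan is that it is descriptive by design. The primary objectives are to estimate EBA in each cohort. The katG hypothesis in protocol 1.1.3 is measurable activity at 15 or 20 mg/kg, not superiority of one dose. Protocol 9.4 calls the Group 3 analysis exploratory, and the three randomized Group 1 doses have no planned pairwise contrast either. All of this stands, and it is why the contrast should remain exploratory. It is not a reason to leave out an interval for an effect the protocol says it will examine.

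The displays are also more than bare orderings. They carry cohort CIs, and the difference can be computed from the tabled N, mean and SD. That stands too, so it would be wrong to say the plan throws the randomization away. What is missing is the prespecified estimate.

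Dose-response is approached through the AUC/MIC model as well. Protocol 2.1 puts fast-acetylator AUC at 30% to 50% of slow, a 2- to 3.3-fold spread against a dose ratio of 20/15 = 1.33, so an exposure model is a sensible tool. But MIC and acetylator status are not randomized, so it does not replace the contrast. The separate PK plan and the Analysis Implementation Plan were not available, so the gap is shown only for the protocol and SAP.

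A reader might infer that the plan has a 50% false-positive rate, because with no dose effect the 20 mg/kg mean is higher half the time. The documents do not support this. They contain no rule that a higher mean counts as a dose effect, and the 50% holds in any two-arm comparison with equal allocation. The same applies to error rates based on non-overlap of the two CIs. Neither document says that a dose will be chosen from the plots.

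**Conclusion.** The point holds as an omission in reporting. Within the protocol and SAP, the one randomized contrast added in Version 3.0 is left to visual displays, and its size and uncertainty are never estimated. At SD 6 and 10 evaluable per dose, the 95% CI of the difference would have a half-width of about 5.6, or 2.8 to 8.5 for assumed SDs of 3 to 9. Against an example mean of 13, the plots cannot separate no effect from a moderate one.

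These figures assume roughly normal data, equal SDs and 10 evaluable per arm. They also assume that an SD from a 14-day endpoint carries over to 7 days, which the documents do not show. The point does not affect the sample size or the cohort-level primary estimates. It is a cheap improvement that should be made, not a fatal flaw.

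**What to change.** 1. **Direction first.** In protocol 9.2.1.2 and SAP 3.2, either reverse the subtraction or state that negative EBA0-7(TTD) means activity. Make the 9.4 example and the model slopes agree with that choice.
2. **Protocol 9.4 and SAP 4.3.1.** Replace the visual-displays sentence in 9.4, and add to SAP 4.3.1:

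> The difference in mean EBA0-7(TTD) between the 20 and 15 mg/kg Group 3 cohorts will be estimated with a two-sided 95% CI (t, 18 df; expected half-width about 5.6 at SD 6) as an exploratory estimate; plots are supportive.

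3. **SAP 4.3.2.** Fit one TTD mixed model to both Group 3 doses with a day-by-dose term, or the matching slope contrast if the nonlinear model is used. Report it with its 95% CI.

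Attach no rule that a dose effect may be claimed only if the interval excludes zero. That would turn an exploratory estimate into a test with little power: at SD 6, 19% for a true difference of 3 and 56% for 6. If Group 3 post-entry data have already been seen, label the addition post hoc, in line with SAP 4.1.

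The cost is a few sentences and an extra table row, with no new participants or data. The downside is that the interval will be wide and will show openly how little 10 per dose can separate the doses.

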The main reason for this CM is to clarify the target accrual for the study. In addition, the ACTG Web site address has been updated, and the laboratory requirement for CD4+ count testing has been updated to comply with the DAIDS policy on Requirements for DAIDS Funded and/or Sponsored Laboratories in Clinical Trials.

The following are clarifications to Protocol A5312, Version 3.0, 08/21/18, titled "The Early Bactericidal Activity of High-Dose or Standard-Dose Isoniazid among Adult Participants with Isoniazid-Resistant or Drug-Sensitive Tuberculosis." These clarifications will be included in the next version of the A5312 protocol if it is amended at a future date.

1. There were 259 total participants enrolled in A5312 prior to the implementation of Version 3.0; this includes 64 participants who were enrolled in Group 3, Step 1. Under Version 3.0, the target accrual for Group 3, Step 2, is 20 participants. Since some participants who screen for the study will qualify for Step 1 and not for Step 2, it is expected that 20 additional participants will enroll in Group 3, Step 1 only. Thus, the total accrual for the study is 299 participants (259 under Version 2.0, and 40 participants under Version 3.0). Participants in Group 3, Step 2, who discontinue before the day 7 sample collection will be replaced and are not included in the calculation for target accrual. Below is the breakdown of enrollment by group and step:

Group	Step	Actual Accrual prior to Version 3.0	Expected Accrual under Version 3.0	Target Accrual (Actual + Expected)
1	1 only	66		66
	1 + 2	44		44
2	1 only	69		69
	1 + 2	16		16
3	1 only	64	20	84
	1 + 2		20	20
				Total: 299

2. Study Management, Copies of the Protocol: The text has been revised to read:

To request hard copies of the protocol, send a message to [contact] via e-mail. Electronic copies can be downloaded from the ACTG Web site (<https://actgnetwork.org>).

3. Section 4.3, Inclusion Criteria for Step 2, Criterion 4.3.6:

For HIV-positive candidates only: CD4+ count of ≥ 50 cells/mm³, performed within 7 days prior to entry at **any network-approved laboratory that is IQA-certified**.

4. Section 6.3, Instructions for Evaluations. The following language has been added as the first paragraph in this section:

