### 1.2 Key Updates to the SAP

Version	Changes Made	Date finalized
1	Original Version	7/2/2018
1	Protocol amendment review (Version 3.0) by [name] and [name]	3/28/2019
2	Review after LOA #1. Updated the protocol overview to describe the LOA and CMs and personnel changes. The plans for analysis are unchanged.	1/21/2021
3	A new lab, BARC, did culture for TASK participants enrolled in protocol Version 3.0 and reported re-cultured results after additional decontamination. These results were not supposed to be reported (were not reported previously) and will be excluded from analysis. Under protocol Version 3.0 TTP is not done in duplicate for each sample so this has been clarified. Clarified that a separate statistical report will be prepared for participants enrolled under protocol Version 3.0. Added [name] to statistical team.	5/5/2022

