### 3.2 Endpoint Definitions

The following is the calculation of log 10 transformed CFU/mL sputum at each time point.

- $\log_{10} \text{CFU/mL} = \log_{10}[(\text{average of CFU/mL}_A \text{ and CFU/mL}_B) \times (\text{dilution factor}) \times 10^{(\text{Dilution})}]$  where the dilution factor is set to 20. CFU/mLA and CFU/mLB are measured from the same sputum sample at a time point.

Example: If CFU/mLA = 150, CFU/mLB = 185, and dilution = 4, then  $\log_{10} \text{CFU/mL} = 7.53$

When multiple TTD results were obtained for a specimen (per Protocol Version 2.0 but not Protocol Version 3.0), the following is the calculation of total TTD.

- The final TTD is the mean of TTDA and TTDB. TTDA and TTDB are measured from the same

sputum sample at a time point. If one of the TTD is missing, the other TTD will be used as the final TTD. In a rare case of observing TTD = 42 days, the sites will determine if the value should be used as is or treated as missing.

The following are definitions from Section 9.2 of the protocol document.

- EBA0-7(CFU)= [baseline log10 CFU/mL sputum (mean of log10 CFU/mL at pre-entry and day 0) – log10 CFU/mL at day 7]/7. For a CFU/ml count of 0, the log10 CFU/mL will be set to 0
- EBA0-7(TTD)= [baseline TTD (mean of TTD at pre-entry and day 0) – TTD at day 7]/7
- EBA0-2(CFU)= [baseline log10 CFU/mL sputum (mean of log10 CFU/mL at pre-entry and day 0) – log10 CFU/mL at day 2]/2. For a CFU/ml count of 0, the log10 CFU/mL will be set to 0
- EBA0-2 (TTD)= [baseline TTD (mean of TTD at pre-entry and day 0) – TTD at day 2]/2.
- EBA2-7(CFU)= (log10 CFU/mL sputum at day 2 – log10 CFU/mL at day 7)/5. For a CFU/ml count of 0, the log10 CFU/mL will be set to 0
- EBA2-7 (TTD)= [TTD at day 2 – TTD at day 7]/5

For Group 3, TTP results from contaminated samples and from TTP from re-culture results after an additional decontamination step will be excluded from analysis.

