### 4.2 Visit Schedule and Analysis Windows

- Screening visit window = within 2 weeks (14 days) prior to Step 1 entry

- Pre-entry visit window = approximately 2 days prior to Step 2 entry
- Step 2 entry visit = Day 0 in Step 2
- On-Treatment evaluations: conducted between Day 1 and Day 7. Participants will be discharged on Day 8.
- Post-Treatment evaluations: completed in a period of plus or minus 3 days from Day 21.

**Note:** Participants who do not complete 7 days of study treatment or who cannot provide at least 1 mL for all required overnight sputum samples through Day 7 will be discontinued from the study, and replaced.

- Schedule of Events

Evaluation	Screening	Pre-entry	Entry: Registration/ Randomization	Study Treatment (Days)							Discharge	Final Visit	Premature Discontinuation	
				Step 2 Day 0	1	2	3	4	5	6	7			
Documentation of HIV status	X													
Medical/Medication History			X											
Complete Physical Examination	X													
Targeted Physical Examination			X	X	X	X	X	X	X	X	X	X	X	X
Karnofsky Score	X													
Height	X													
Weight	X		X	X	X	X	X	X	X	X	X	X	X	X
Signs/Symptoms/ Diagnoses			X	X	X	X	X	X	X	X	X	X	X	X
Concomitant/TB/ ARV Medications			X	X	X	X	X	X	X	X	X	X	X	X
Complete Blood Count with Differential	X		X							X		X		X
Complete Blood Chemistry Profile	X		X							X		X		X
CD4+ Count (HIV-infected participants)	X													
Pregnancy Test	X 		X											
NAT2 genotype (blood and saliva)			X											
Chest X-ray	X 													
Spot Sputum Collection			X 											
Genotypic DST			X											

Evaluation	Screening	Pre-entry	Entry: Registration/ Randomization	Study Treatment (Days)							Discharge	Final Visit	Premature Discontin- uation	
				Step 2 Day 0	1	2	3	4	5	6	7			
(MTBDRs) 														
Overnight Sputum Collection		X	X		X	X	X	X	X	X	X			
EBA Analysis by Solid Culture CFU Determination and Liquid MGIT Culture for TTD 		X	X		X	X	X	X	X	X	X			
Pharmacokinetic Sampling										X				
Hospitalization	X 	X	X		X	X	X	X	X	X	X			

Participants must have a negative serum or urine pregnancy test within 7 days prior to entry.

A chest x-ray is not required at screening if results of a chest x-ray performed within 14 days prior to screening are available.

Sputum from Step 1 (Screening or Day 0) may be used if there is an adequate amount for genotypic DST.

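### No replacement rule covers a contaminated Day 7 culture, so a Group 3 cohort can reach its 10 completers with fewer than 10 primary EBA0-7(TTD) values, and the precision given for n=10 holds only if no needed culture fails

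*Protocol*

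**What the plan says.** **Replacement.** Protocol 9.4 (Accrual) states that "participants who discontinue the study prior to the Day 7 evaluations will be replaced" and gives maintaining the precision of the primary analyses as the purpose. Clarification Memo #1 to Version 3.0 (item 1) applies this to the new cohorts: "Participants in Group 3, Step 2, who discontinue before the day 7 sample collection will be replaced". SAP 4.2 goes further. It also replaces anyone who does not complete the 7 days of treatment, and says that those "who cannot provide at least 1 mL for all required overnight sputum samples through Day 7 will be discontinued from the study, and replaced". Protocol 8.1 lists failure to provide a required sputum sample as a reason for discontinuation. A failed culture is not on that list.

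**Target.** The protocol synopsis says "20 evaluable participants (10 completing treatment in each dosing cohort) will be randomized", so evaluable is explained as completing treatment. For Step 1, by contrast, 9.4 defines evaluable by the availability of the required data.

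**Endpoint.** For Group 3 the primary efficacy endpoint is EBA0-7(TTD) alone (protocol 9.2.1; TTD is also written TTP). It needs a Day 7 value and a baseline, which is the mean of the pre-entry and Day 0 values. SAP 3.1 limits the primary analysis to participants with CFU and TTD data at both entry and Day 7. SAP 1.2 records that "Under protocol Version 3.0 TTP is not done in duplicate for each sample", and SAP 3.2 that for Group 3 "TTP results from contaminated samples and from TTP from re-culture results after an additional decontamination step will be excluded from analysis".

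**The concern.** The rules act on the participant and the specimen, while the endpoint depends on the culture result. By footnote 5 of the Step 2 schedule, the Day 7 overnight collection is assayed the next morning, and discharge is on Day 8. Contamination can therefore come to light only when the participant has already completed, and a rule keyed to discontinuation or sputum volume cannot respond.

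Group 3 is more exposed than the earlier groups. Under Version 2.0 a missing TTD could be covered by its duplicate, and CFU was a second endpoint. Under Version 3.0 neither holds. A participant can count toward the 10 and have no EBA0-7(TTD). What is at stake is the number behind each Group 3 primary estimate, and whether the precision stated for n=10 describes the analysis that will be done.

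**Working it through.** **1. The plan's own figure.** Inputs from protocol 9.4: SD 6, n=10, example mean 13. Half-width = quantile × SD / √n.

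- Normal: 1.96 × 6 / √10 = 3.72, so the interval is 13 ± 3.72 = 9.28 to 16.72. This reproduces the stated 9.28 to 16.7.
- t, 9 df: 2.262 × 6 / √10 = 4.29, giving 8.71 to 17.29.

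The half-width printed in the same paragraph, 0.086, does not follow from SD 6. It matches 2.262 × 0.12 / √10 = 0.0858, the Table 9.4-1 entry for SD 0.12. That is a separate slip. The plan's precision is taken here as 3.72.

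**2. Effect of unreplaced losses.** The quantile is kept the same within each column, so that the loss is not mixed with the choice between normal and t.

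| n with EBA0-7(TTD) | Normal | Change | t (n−1 df) | Change |
|---|---|---|---|---|
| 10 | 3.72 | – | 4.29 | – |
| 9 | 3.92 | +5% | 4.61 | +7% |
| 8 | 4.16 | +12% | 5.02 | +17% |

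**3. How likely a loss is.** The documents give no contamination rate. Assume a rate c per culture, independent between samples. The chance that a cohort of 10 loses at least one Day 7 result is 1 − (1 − c)^10:

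- c = 5%: 40%
- c = 10%: 65%
- c = 15%: 80%

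**4. Effect of the definition.** Compare two rules, leaving out the CFU condition.

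- Valid Day 0 and Day 7 (the TTD part of SAP 3.1, reading study entry as Day 0): (1 − c)² = 0.9025, 0.81, 0.7225. Expected per cohort of 10: 9.0, 8.1, 7.2.
- Valid Day 7 and at least one of the two pre-treatment samples: (1 − c²)(1 − c) = 0.948, 0.891, 0.831. Expected: 9.5, 8.9, 8.3.

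**5. Cost of restoring 20 by replacement under the second rule.** 20/0.948 = 21.1, 20/0.891 = 22.4 and 20/0.831 = 24.1. That is about 1, 2-3 or 4 extra participants in total at 5%, 10% or 15%.

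**The case against.** A reader might infer three stronger things that the documents do not support.

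- **That leaving before Day 7 is the only trigger.** SAP 4.2 adds incomplete treatment and inadequate sputum volume. The uncovered case is narrower: an adequate sample whose culture fails.
- **That the participant contributes nothing.** SAP 3.1 keeps every randomized participant with at least one TTD in the model-based analysis, and SAP 4.3.2 models TTD from all time points. SAP 4.1 also anticipates missing baseline or Day 7 results and says the model might then be more appropriate. Safety and PK data remain as well. What is lost is the EBA0-7(TTD) value.
- **That the stated size will not be delivered.** That size is in terms of participants completing treatment, and the rules can deliver it. SAP 1.2 records re-culture results after additional decontamination. It does not say how often this happened, on which days, or that anyone lost a Day 7 value.

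It can also be said that little depends on this. Protocol 9.4 calls the Group 3 per-cohort analysis exploratory, and any dose effect is to be examined visually. The SD of 6 is borrowed from EBA0-14 in another study, so a 5-7% widening is small beside that uncertainty. This limits the weight of the point but does not close the gap. EBA0-7(TTD) in Group 3 is still listed as a primary objective and endpoint, and the remark in SAP 4.1 sets no rule and restores no observations.

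**Conclusion.** The gap is real and modest in size. Replacement is justified by the precision of the primary analyses, yet no rule responds to a contaminated culture from an adequate Day 7 sample. The participant then counts toward the 10 without a primary EBA0-7(TTD). The n=10 precision is therefore conditional on no needed culture failing, and the plan does not say so. One loss in a cohort widens the interval by about 5-7%, and two by about 12-17%.

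These percentages rest only on n and the choice of quantile, because the SD cancels. The absolute half-widths also rest on SD 6. Any statement of how often losses occur rests on assumed rates and on independence between samples.

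The definition of the analysis set matters as much as replacement. Read literally, SAP 3.1 requires CFU data that Group 3 does not have. Its entry requirement would also drop a participant whose Day 0 culture alone failed although the pre-entry culture was valid.

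**What to change.** 1. In SAP 3.1 and protocol 9.4, define the Group 3 evaluable set for EBA0-7(TTD) as a valid Day 7 TTD plus at least one valid pre-treatment TTD, with no CFU requirement. State in the endpoint definition (protocol 9.2.1.2, SAP 3.2) that a single valid pre-treatment value serves as the baseline when the other is unusable.
2. In protocol 9.4, say that the n=10 precision assumes no unusable cultures. Give the half-widths at n=9 and n=8 beside it, with one quantile throughout: 3.72, 3.92 and 4.16 (normal), or 4.29, 4.61 and 5.02 (t).
3. Optional, while accrual is open: tie replacement to the definition in item 1. At assumed rates of 5%, 10% or 15% this needs about 1, 2-3 or 4 extra participants in total.

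Items 1 and 2 cost wording only. The small downside of item 1 is that some baselines rest on one sample instead of the mean of two, and are a little noisier. If accrual has closed, items 1 and 2 are enough.
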